8.2.6. Quality of Life/Impact of Dry Eye on Everyday Life (IDEEL)

The IDEEL questionnaire will be filled in at screening, baseline-Day1, Week 4, Week 8, Week 12 and Week16.

IDEEL is a 3-module questionnaire with 57 questions, and it assesses dry eye symptoms, the effect of dry eye disease on quality of life, and treatment satisfaction over the last 2 weeks. The 3 modules consist of:

- Dry eye Quality of Life (27 questions) comprising three sections: "Daily activities", "Feelings" and "Work".
- Dry eye Treatment satisfaction & Bother (10 questions) comprising two sections: "Treatment – In general" and "Treatment- Eye drop".
- Dry eye Symptom bother (20 questions).

Module 1:

Dry eye impact on daily life (27 questions) comprising 3 QOL domains: 1.a "Daily activities limitations", 1.b "Emotional well being" and 1.c "Work limitations".

26 questions will be considered as part of one of these 3 domains. Question 22 will not be considered part of a domain.

1.a: Daily Activities

| Daily activities section | QOL content domain | Variable Name | Used in calculation of domain score? |
|---|----------------------------|---------------|--------------------------------------|
| 1. Doing close work in the morning or afternoon (such as crossword puzzles, reading, looking at a computer, and/or sewing) | Daily Activity Limitations | IDLACT1 | Yes |
| 2. Doing close work in the evening or at night | Daily Activity Limitations | IDLACT2 | Yes |
| 3. Driving | Daily Activity Limitations | IDLACT3 | Yes |
| 4. Being around and/or using scented products (such as cologne or hairspray) | Daily Activity Limitations | IDLACT4 | Yes |
| 5. Working on a computer | Daily Activity Limitations | IDLACT5 | Yes |
| 6. Going somewhere where there is tobacco smoke or being around someone who smokes | Daily Activity Limitations | IDLACT6 | Yes |
| 7. Wearing contact lenses | Daily Activity Limitations | IDLACT7 | No |
| 8. Wearing make-up near or on my eyes | Daily Activity Limitations | IDLACT8 | No |

This document is confidential.

| Daily activities section | QOL content domain | Variable Name | Used in calculation of domain score? |
|--------------------------|----------------------------|---------------|--------------------------------------|
| 9. Flying on an airplane | Daily Activity Limitations | IDLACT9 | No |

| Response for questions 1 to 9 (IDLACT1-IDLACT9) | Original response code | Item score |
|---|------------------------|------------|
| I did not do this activity for reasons other than my dry eyes | 6 | 5 |
| None of the time | 5 | 5 |
| A little of the time | 4 | 4 |
| Some of the time | 3 | 3 |
| Most of the time | 2 | 2 |
| All of the time | 1 | 1 |
| I can no longer do this activity due to my dry eyes | 0 | 0 |

The response option “I did not do this activity for reasons other than my dry eyes” has a response coded 6 but a scored item value of 5.

The original response code is the value to be used for data-entry. The item score is used during the computation of the Daily Activity Limitations Scale Score. Higher item scores are intended to reflect better quality of life (i.e. less limitations on daily activities).

Only 6 questions (9 (IDLACT1-IDLACT6) are included in the Daily activity Limitations scale score. Questions 7, 8 and 9 are excluded.

If 50% (3) or fewer of the 6 questions used in calculating Daily Activity Limitations score have missing item score, then the scale score is calculated by multiplying the mean of the non missing item score by 20. If 4 or more of the 6 item scores are missing then the scale score is not calculated and should be set at missing.

Multiplying by 20 transforms the scale score to a 0 to 100 scale, with 0 reflecting the greatest degree of limitations on daily activities measurable by the scale and 100 reflecting the greatest freedom from limitations on daily activities.

1.b Feelings

| Feelings | QOL content domain | Variable Name | Used in calculation of domain score? |
|---|----------------------|---------------|--------------------------------------|
| 10. Irritability | Emotional Well-Being | IDLEMO1 | Yes |
| 11. Impatience | Emotional Well-Being | IDLEMO2 | Yes |
| 12. Feeling sad | Emotional Well-Being | IDLEMO3 | Yes |
| 13. Worry that my dry eyes will get worse | Emotional Well-Being | IDLEMO4 | Yes |

This document is confidential.

| Feelings | QOL content domain | Variable Name | Used in calculation of domain score? |
|---|----------------------|---------------|--------------------------------------|
| 14. Feeling annoyed | Emotional Well-Being | IDLEMO5 | Yes |
| 15. Feeling like my eyes do not look nice | Emotional Well-Being | IDLEMO6 | Yes |
| 16. Feeling like I have to make adjustments to my life | Emotional Well-Being | IDLEMO7 | Yes |
| 17. Feeling different from other people because of my dry eyes | Emotional Well-Being | IDLEMO8 | Yes |
| 18. Feeling like I am always aware of my eyes | Emotional Well-Being | IDLEMO9 | Yes |
| 19. Feeling older than I really am | Emotional Well-Being | IDLEMO10 | Yes |
| 20. Feeling like people look at me and think I am fine when I'm not | Emotional Well-Being | IDLEMO11 | Yes |
| 21. Feeling like there is nothing I can do for my dry eyes | Emotional Well-Being | IDLEMO12 | No |

| Response for questions 10 to 21 | Original response code | Item score |
|---------------------------------|------------------------|------------|
| None of the time | 4 | 4 |
| A little of the time | 3 | 3 |
| Some of the time | 2 | 2 |
| Most of the time | 1 | 1 |
| All of the time | 0 | 0 |

11 questions (IDLEMO1- IDLEMO11) are included in the Emotional Well-Being score. Question 21 (IDLEMO12) is excluded from calculation.

If 50% (5) or fewer of the 11 questions used in the calculation of Emotional Well-Being score have missing item score, then the scale score is calculated by multiplying the mean of the non missing item scores by 25. If 6 or more of the 11 item scores are missing then the scale score is not calculated and should be set at missing.

Multiplying by 25 transforms the scale score to a 0 to 100 scale, with 0 reflecting the worst level of emotional well-being measurable by the scale and 100 reflecting the best.

1.c Work

| Work | QOL content domain | Variable Name | Used in calculation of domain score? |
|--------------------------------|--------------------|---------------|--------------------------------------|
| 22. Are you currently working? | Work limitations | IDLWRKYN | - |

This document is confidential.

| Work | QOL content domain | Variable Name | Used in calculation of domain score? |
|--|--------------------|---------------|--------------------------------------|
| 23. Feeling distracted | Work limitations | IDLWRK1 | Yes |
| 24. Feeling like I couldn't concentrate | Work limitations | IDLWRK2 | Yes |
| 25. Having to take a break from work | Work limitations | IDLWRK3 | Yes |
| 26. Having to change the way I work (such as the way I read, look at a computer, or work outside) | Work limitations | IDLWRK4 | Yes |
| 27. Having to change my work environment (such as how close I am to an air conditioning or heating vent) | Work limitations | IDLWRK5 | Yes |

| Response for question 22 (IDLWRKYN) | Original response code | Item score |
|-------------------------------------|------------------------|------------|
| Yes | 1 | 1 |
| No | 0 | 0 |

| Response for questions 23 to 27 (IDLWRK1-IDLWRK5) | Original response code | Item score If IDLWRKYN=0 | Item score If IDLWRKYN=1 |
|---|------------------------|--------------------------|--------------------------|
| None of the time | 4 | Missing | 4 |
| A little of the time | 3 | Missing | 3 |
| Some of the time | 2 | Missing | 2 |
| Most of the time | 1 | Missing | 1 |
| All of the time | 0 | Missing | 0 |

5 questions (IDLWRK1-IDLWRK5) are included in the Work Limitations domain..

If 50% (2) or fewer of the 5 questions used in the calculation of the Work Limitations score have missing item scores, then the scale score is calculated by multiplying the mean of the non missing item scores by 25. If 3 or more of the 5 item scores are missing then the scale score is not calculated and should be set to missing.

Multiplying by 25 transforms the scale score to a 0 to 100 scale, with 0 reflecting the greatest degree of limitation at work measurable by the scale and 100 reflecting the least limitation at work.

Module 2:

Dry eye Treatment satisfaction & Bother module (10 questions) comprising 2 QoL domains: 2.a “Treatment satisfaction / Happiness” and “Treatment-related bother”.

2.a Treatment - In general

This document is confidential.

| Treatment in General | QOL content domain | Variable Name | Used in calculation of domain score? |
|--|-----------------------------------|---------------|--------------------------------------|
| 1. OVER THE LAST TWO WEEKS , how often did you use treatment for your dry eyes? | - | IDLTREAT | - |
| 2. I was happy with how quickly my treatments worked | Treatment Satisfaction/ Happiness | IDLTS1 | Yes |
| 3. I was happy with how long the effects of my treatments lasted | Treatment Satisfaction/ Happiness | IDLTS2 | Yes |
| 4. The treatments I used completely eliminated my dry eye symptoms | Treatment Satisfaction/ Happiness | IDLTS3 | Yes |
| 5. The treatments I used relieved most of my dry eye symptoms | Treatment Satisfaction/ Happiness | IDLTS4 | Yes |
| 6. I was bothered by how often I had to use dry eye treatments | Treatment- Related Bother | IDLTBO1 | Yes |

| Response for question 1 (IDLTREAT) | Original response code | Item score |
|------------------------------------|------------------------|------------|
| None of the time | 0 | 0 |
| A little of the time | 1 | 1 |
| Some of the time | 2 | 2 |
| Most of the time | 3 | 3 |
| All of the time | 4 | 4 |

| Response for questions 2 to 5 (IDLTS1- IDLTS4) | Original response code | Item score If IDLTREAT=0 | Item score If IDLTREAT NE 0 or missing |
|--|------------------------|--------------------------|--|
| None of the time | 0 | Missing | 0 |
| A little of the time | 1 | Missing | 1 |
| Some of the time | 2 | Missing | 2 |
| Most of the time | 3 | Missing | 3 |
| All of the time | 4 | Missing | 4 |
| Response for question 6 (IDLTBO1) | | | |
| None of the time | 4 | Missing | 4 |
| A little of the time | 3 | Missing | 3 |
| Some of the time | 2 | Missing | 2 |
| Most of the time | 1 | Missing | 1 |
| All of the time | 0 | Missing | 0 |

4 questions (IDLTS1 - IDLTS4) are included in the Treatment Satisfaction/Happiness scale score.

This document is confidential.

If 50% (2) or fewer of the 4 questions used in the calculation of Treatment Satisfaction/Happiness score have missing item score, then the scale score is calculated by multiplying the mean of the non missing item score by 25. If 3 or more of the 4 item scores are missing then the scale score is not calculated and should be missing.

Multiplying by 25 transform the scale score to a 0 to 100 scale, with 0 reflecting the lowest level of satisfaction/happiness with treatment measurable by the scale and 100 reflecting the highest level of satisfaction/happiness with treatment..

2.b Treatment- Eye Drops

| Treatment- Eye Drops | QOL content domain | Variable Name | Used in calculation of domain score? |
|--|---------------------------|---------------|--------------------------------------|
| 7. Do you ever use eye drops to treat your dry eyes? | - | IDLDRPYN | - |
| 8. I was bothered by blurriness shortly after using my eye drops | Treatment- Related Bother | IDLTBO2 | Yes |
| 9. I was embarrassed when I had to use my eye drops | Treatment- Related Bother | IDLTBO3 | Yes |
| 10. I felt like I could not go anywhere without my eye drops | Treatment- Related Bother | IDLTBO4 | Yes |

| Response for question 1 (IDLDRPYN) | Original response code | Item score |
|------------------------------------|------------------------|------------|
| Yes | 1 | 1 |
| No | 0 | 0 |

| Response for question 8 to 10 (IDLTBO2- IDLTBO4) | Original response code | Item score If IDLDRPYN=0 | Item score If IDLDRPYN NE 0 |
|--|------------------------|--------------------------|-----------------------------|
| None of the time | 4 | Missing | 4 |
| A little of the time | 3 | Missing | 3 |
| Some of the time | 2 | Missing | 2 |
| Most of the time | 1 | Missing | 1 |
| All of the time | 0 | Missing | 0 |

4 questions (IDLTBO1 - IDLTBO4) are included in the Treatment-Related Bother scale score.

If 50% (2) or fewer of the 4 questions used in the calculation of Treatment-Related Bother scale score have missing item scores, then the scale score is calculated by multiplying the mean of the non missing item score by 25. If 3 or more of the 4 item scores are missing then the scale score is not calculated and should be set at missing.

Multiplying by 25 transforms the scale score to a 0 to 100 scale, with 0 reflecting the greatest degree of treatment related bother measurable by the scale and 100 reflecting the lowest degree of treatment-related bother.

This document is confidential.

Module 3:

Dry eye Symptom bother (20 questions) comprising a unique domain.

| Symptom Bother | QOL content domain | Variable Name | Used in calculation of domain score? |
|---|--------------------|---------------|--------------------------------------|
| 1.OVER THE LAST TWO WEEKS , how often did you experience dry eye symptoms? | Symptom Bother | IDLSYM1 | Yes |
| 2. Eyes that felt gritty or sandy | Symptom Bother | IDLSYM2 | Yes |
| 3. Felt like I needed to close my eyes even though I was not tired | Symptom Bother | IDLSYM3 | Yes |
| 4. Burning or stinging eyes | Symptom Bother | IDLSYM4 | Yes |
| 5. Tired eyes | Symptom Bother | IDLSYM5 | Yes |
| 6. Blurry vision | Symptom Bother | IDLSYM6 | Yes |
| 7. Itchy eyes | Symptom Bother | IDLSYM7 | Yes |
| 8. Irritated eyes | Symptom Bother | IDLSYM8 | Yes |
| 9. Eyes that felt like they had been scratched by something | Symptom Bother | IDLSYM9 | Yes |
| 10. Eye dryness | Symptom Bother | IDLSYM10 | Yes |
| 11. Mucus in, around, or coming out of my eyes | Symptom Bother | IDLSYM11 | Yes |
| 12. Puffy or swollen eyes | Symptom Bother | IDLSYM12 | Yes |
| 13. Eye redness | Symptom Bother | IDLSYM13 | Yes |
| 14. Aching or sore eyes | Symptom Bother | IDLSYM14 | Yes |
| 15. Felt like something was in my eye | Symptom Bother | IDLSYM15 | Yes |
| 16. Frequent and/or rapid blinking | Symptom Bother | IDLSYM16 | Yes |
| 17. Difficulty blinking because of little or no moisture in my eyes | Symptom Bother | IDLSYM17 | Yes |
| 18. Sensitivity to light, glare, and/or wind | Symptom Bother | IDLSYM18 | Yes |
| 19. Sensitivity to recirculated air (such as air conditioning and heat) | Symptom Bother | IDLSYM19 | Yes |
| 20. Headaches associated with dry eye symptoms | Symptom Bother | IDLSYM20 | Yes |

This document is confidential.

| Response for question 1 (IDLSYM1) | Original response code | Item score |
|-----------------------------------|------------------------|------------|
| None of the time | 0 | 0 |
| A little of the time | 1 | 1 |
| Some of the time | 2 | 2 |
| Most of the time | 3 | 3 |
| All of the time | 4 | 4 |

| Response for questions 2 to 20 (IDLSYM2 - IDLSYM20) | Original response code | Item score |
|---|------------------------|------------|
| I did not have this symptom / Not applicable | 0 | 0 |
| Not at all | 1 | 1 |
| Slightly | 2 | 2 |
| Moderately | 3 | 3 |
| Very much | 4 | 4 |

All questions (IDLSYM1 – IDLSYM20) are included in the Symptom Bother scale score (IDLSYM).

If 50% (10) or fewer of the 20 questions used in the calculation of Symptom Bother scale score have missing item scores, then the scale score is calculated by multiplying the mean of the non missing item score by 25. If 11 or more of the 20 item scores are missing then the scale score is not calculated and should be set at missing.

Multiplying by 25 transforms the scale score to a 0 to 100 scale, with 0 reflecting the greatest degree of treatment related bother measurable by the scale and 100 reflecting the lowest degree of treatment-related bother.

Changes from baseline in each scale score will be analyzed using an mixed model for repeated measures (MMRM). The analyses will include the fixed, categorical effects of treatment (3 levels: rhNGF 20 µg/ml TID, rhNGF 20 µg/ml BID and vehicle TID), visit (4 levels: Weeks 4, 8, 12, 16) and treatment by visit interaction. Subject will be considered as a random effect. The covariance matrix used will be "unstructured". Comparisons versus vehicle TID will be provided using least square means at each visit and overall.

IDEEL data will be also listed.

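### The printed anchors for the IDEEL Symptom Bother score (SAP 8.2.6, Module 3) run opposite to the SAP's own item scoring

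*SAP*

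**What the plan says.** IDEEL is a secondary efficacy endpoint (SAP 4.2; Protocol 7.1.2). SAP 8.2.6 defines six scale scores, each on a 0 to 100 range.

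For Symptom Bother (Module 3), item 1 is scored from 0 for none of the time to 4 for all of the time. Items 2 to 20 start at "I did not have this symptom / Not applicable | 0 | 0" and rise to 4 for very much. In every row the response code and the item score are the same. All 20 items enter the score, and the missing-item rule is stated ("If 50% (10) or fewer of the 20 questions used in the calculation of Symptom Bother scale score have missing item scores"), after which the mean of the non-missing items is multiplied by 25. The SAP then describes the result as a scale "with 0 reflecting the greatest degree of treatment related bother measurable by the scale and 100 reflecting the lowest degree of treatment-related bother".

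The same words appear at the end of Module 2, where "4 questions (IDLTBO1 - IDLTBO4) are included in the Treatment-Related Bother scale score".

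Change from baseline in each scale score is analysed by MMRM, and "Comparisons versus vehicle TID will be provided using least square means at each visit and overall".

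**The concern.** The scoring table and the sentence interpreting it cannot both be right. The sentence also names the wrong construct, which suggests it was carried over from Module 2 without being adapted.

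The printed anchors of the other five scales all put the best state at 100. For example, Daily Activity Limitations has "100 reflecting the greatest freedom from limitations on daily activities", Emotional Well-Being is described "with 0 reflecting the worst level of emotional well-being measurable by the scale and 100 reflecting the best", and Work Limitations has "100 reflecting the least limitation at work". The Module 3 sentence makes Symptom Bother look aligned with these, while its item coding makes it the only scale on which a higher score is worse.

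Two things could go wrong. A reader who relies on the printed anchors would take a fall in Symptom Bother as deterioration and a rise as improvement. A programmer who trusts the sentence over the table could reverse the score, which would change the sign of every reported difference on this scale.

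**Working it through.** **Inputs (all from SAP 8.2.6).** Item score ranges, items included and multiplier for each scale. Score = mean of item scores × multiplier, evaluated at the most and least favourable response patterns.

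| Scale | Items × multiplier | Worst pattern | Best pattern | Printed meaning of 100 | Agrees? |
|---|---|---|---|---|---|
| Daily Activity Limitations | 6 items, × 20 | 0 × 20 = 0 | 5 × 20 = 100 | best | yes |
| Emotional Well-Being | 11 items, × 25 | 0 × 25 = 0 | 4 × 25 = 100 | best | yes |
| Work Limitations | 5 items, × 25 | 0 × 25 = 0 | 4 × 25 = 100 | best | yes |
| Treatment Satisfaction/Happiness | 4 items, × 25 | 0 × 25 = 0 | 4 × 25 = 100 | best | yes |
| Treatment-Related Bother | 4 items, × 25 | all of the time: 0 × 25 = 0 | none of the time: 4 × 25 = 100 | least bother | yes |
| Symptom Bother | 20 items, × 25 | all of the time plus 19 × very much: 4 × 25 = 100 | none of the time plus 19 absent symptoms: 0 × 25 = 0 | least bother | **no** |

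The stated 0 to 100 range is reproduced for Symptom Bother, but the stated direction is not. With all 20 items at 0, 1, 2, 3 or 4 the score is 0, 25, 50, 75 or 100, rising with severity.

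**Effect on a treatment difference (responses assumed for illustration).** Both arms start with every item at 3, a score of 3 × 25 = 75. The active arm moves to 2 on every item, a score of 50, and vehicle does not change.

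- Scored as tabulated: (50 − 75) − (75 − 75) = −25. This is a benefit under the item coding and a harm under the printed anchors.
- If a programmer reverses the score as 100 − score to fit the sentence: (50 − 25) − (25 − 25) = +25. The magnitude is the same and the sign is opposite.

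**Number of contrasts affected.** 2 active arms × (4 visits + 1 overall) = 10 per analysis set. SAP 8 calls for secondary endpoints in both the FAS and the Per Protocol set, and the IDEEL tables are indexed for both, so the count is 10 × 2 = 20 if the MMRM is run in each.

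**Does anything else in the SAP settle the direction?** No. SAP 6.3.1 refers to the questionnaire manuals for missing data only. SAP 11 changes the IDEEL analysis method but says nothing about scoring. The IDEEL sample code in Appendix I models the change score with no reversal step and no statement of which direction is favourable.

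**The case against.** The strongest objection concerns weight. The item codes, item list, missing-item rule and multiplier fully specify the score, so it can be computed without the faulty sentence. No planned IDEEL computation depends on direction: there is no responder cut-off or success rule, and the Williams procedure, which does assume an ordering, is not applied to IDEEL in the SAP. A careful reader would see treatment bother named under a symptom module and recognise carried-over text. Independent double programming (SAP 14) makes a lone misreading less likely to pass. The table templates are in a separate document (SAP 6.1), so it is not known that any output repeats the wrong direction. The IDEEL tables are not marked Topline, and symptoms are also covered by SANDE, whose direction SAP 8.2.1 states correctly.

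Most of this stands, and it keeps the point well below a threat to the analysis. It does not remove the contradiction. The anchor sentence is the only text in the SAP that says how to interpret this score, and it is wrong given the item table beside it. Double programming compares numbers: two programs that both follow the item table will agree while the interpretation remains inverted. The objection that the manual might support the printed direction is fair, and the fix allows for it.

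**Conclusion.** The inconsistency is real and confined to Module 3; the identical sentence in Module 2 is correct and should stay. It inverts the interpretation of one of six IDEEL scales, with 10 vehicle contrasts per analysis set (20 if both sets are modelled) open to being read with the wrong sign. Provided the score is computed as tabulated, no estimate, interval or p-value changes, and the primary endpoint and sample size are untouched. The conclusion rests only on the SAP's own scoring table and formula. Which side is wrong, the items or the sentence, cannot be settled without the questionnaire manual, though the misnamed construct points to the sentence. It should be corrected because it is the reading rule for a secondary endpoint; it does not put the trial's main conclusions at risk.

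**What to change.** 1. Check the Module 3 item coding against the IDEEL questionnaire manual.
2. If the coding stands as tabulated, replace the Module 3 anchor sentence only, along these lines: *0 reflects the least and 100 the greatest degree of symptom bother; a negative change from baseline is an improvement.*
3. If the manual reverses the items, correct the item table, or add an explicit 100 − score step, so that it agrees with the anchors.
4. State the favourable direction in a footnote to Tables 14.2.2.6.1 to 14.2.2.6.6. If the coding stands, the footnote should say that Symptom Bother runs opposite to the other five scales.

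The cost is one check against the manual, one corrected SAP sentence (or item table) and one table footnote. If the coding stands, no analysis or programming of the score changes.

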### 4.1. INCLUSION CRITERIA

To be eligible for inclusion into this study, each patient must fulfil the following inclusion criteria:

- 1. Male or female aged  $\geq$  18 years
- 2. Patients with moderate to severe dry eye characterized by the following clinical features:
  - a. Corneal and/or conjunctival staining with fluorescein using National Eye Institute (NEI) grading system > 3
  - b. SANDE questionnaire >25 mm
  - c. Schirmer test I (without anaesthesia) >2 mm <10 mm/5 minutes
  - d. Tear film break-up time (TFBUT) < 10 seconds in the worse eye
- 3. The same eye (eligible eye) must fulfill all the above criteria

- **4.** Patients diagnosed with dry eye at least 6 months before enrolment (current use or recommended use of artificial tears for the treatment of Dry Eye)
- 5. Best corrected distance visual acuity (BCDVA) score of  $\geq 0.1$  decimal units (20/200 Snellen value) in both eyes at the time of study enrolment
- **6.** If a female of childbearing potential, have a negative pregnancy test
- 7. Only patients who satisfy all Informed Consent requirements may be included in the study. The patient and/or his/her legal representative must read, sign and date the Informed Consent document before any study-related procedures are performed. The Informed Consent form signed by patients and/or legal representative must have been approved by the IRB for the current study
- **8.** Patients must have the ability and willingness to comply with study procedures.
- 9. Primary Sjögren's Syndrome Patients:
  - patients with a documented diagnosis of Primary Sjögren's Syndrome according the American-European Consensus Group Sjögren's Syndrome Criteria (Appendix 3; must meet either 4 out of 6 total criteria OR 3 out of 4 signs). Note: Subjects who are on systemic (oral) therapy for the treatment of Sjögren's Syndrome must be on stable systemic treatment defined as the same treatment for the immediately prior 90 days.

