6.2. Key Definitions

6.2.1. Baseline Value

Unless otherwise specified, the baseline value for any variable will be the last value taken prior to the start of medication. This includes screening assessment. Unscheduled measurements prior to first administration date will be considered in the calculation of baseline values.

6.2.2. Change from Baseline and Percent Change from Baseline at a Post-Treatment Time Point

Change from baseline is defined as the difference between the post-treatment value and the baseline value.

Percent change from baseline is defined as $100^* (\text{change from baseline}) / \text{score at baseline}$.

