3) Sample Code for Exploratory sensitivity Efficacy Analysis : Schirmer test I

```
PROC MIXED DATA=SCHIRMERI;
CLASS STRATA TRT01P ;
MODEL chg = TRT01P STRATA STRATA*TRT01P /solution;
lsmeans STRATA*TRT01P / pdiff cl at time=Week4;
```

4) Sample Code for Efficacy Analysis : IDEEL and EQ-5D-3L

```
PROC MIXED DATA=IDEEL;
CLASS usubjid TRT01P visit;
MODEL chg = TRT01P visit TRT01P * visit /ddfm=kr;
repeated visit / sub = usubjid type = un;
lsmeans TRT01P*visit / cl pdiff;
lsmeans TRT01P / cl pdiff;
```

5) Sample Code for Efficacy Analysis: PGIC

A Wilcoxon rank sum test will be used for PGIC. An example of the SAS code to perform this analysis is reported below.

```
*****
```

* SAS Code: Wilcoxon

* Variables in the model:

* aval = value of PGIC

*trt01pn = treatment planned

```
*****;
```

```
PROC NPAR1WAY DATA=PGIC WILCOXON;
WHERE TRT01P in ("Placebo" "Dose 1");
CLASS TRT01P;
VAR AVAL;
RUN;
```

6) Sample Code for Efficacy Analysis: Proportion of subjects with worsening in SANDE and/or NEI score>=50%

```
*****
```

This document is confidential.

* SAS Code: Wilcoxon

* Variables in the model:

* aval = worsening in symptom scores (SANDE) and/or NEI score $\geq 50\%$: yes or No

*trt01pn = treatment planned

*****;

```
PROC FREQ DATA=Prop;
  WHERE TRT01P in ( "Placebo" "Dose 1");
  TABLES trt01p*aval / chisq;
  RUN;
```

This document is confidential.

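### IDEEL Treatment Satisfaction: analysing change from baseline drops patients who reported no treatment before dosing, even when their Week 4 score is complete

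*SAP*

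**What the plan says.** SAP 8.2.6 applies one rule to every IDEEL scale: "Changes from baseline in each scale score will be analyzed using an mixed model for repeated measures (MMRM". The sample code in SAP Appendix I, item 4, has the change as response and no baseline term: "MODEL chg = TRT01P visit TRT01P * visit /ddfm=kr". SAP 6.2.2 needs both values: "Change from baseline is defined as the difference between the post-treatment value and the baseline value".

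The scoring of Module 2, also in SAP 8.2.6, depends on a gate question: "how often did you use treatment for your dry eyes", asked over the last two weeks. The item table has separate columns headed "Item score If IDLTREAT=0 | Item score If IDLTREAT NE 0 or missing". In the first column every response to the four satisfaction items becomes missing. The scale rule follows: "If 3 or more of the 4 item scores are missing then the scale score is not calculated and should be missing".

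Four other provisions matter:
- SAP 6.2.1 takes as baseline the last value before medication and lets a screening value count. IDEEL is completed at both screening and Day 1.
- SAP 6.3.1 lists the variables that receive LOCF. IDEEL is not among them and is referred to its manual.
- Protocol 4.1, criterion 4, accepts "current use or recommended use of artificial tears for the treatment of Dry Eye".
- Protocol 6.1 permits artificial tears in the wash-out but does not require them.

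**The concern.** The satisfaction scale rates a treatment, so a patient who used none has nothing to rate. The scoring rule respects this by leaving the score missing. The analysis rule does not allow for it, because it needs a pre-dose score from everyone. A patient who enters on a recommendation to use tears, and has not used them, lacks that score. By Week 4 the same patient has been assigned drops three times daily for four weeks and can rate them, yet the planned model cannot use the rating.

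Two things are at stake: precision, and whether the result describes the randomised population or only those already treating their dry eye. The SAP also does not say whether a Day 1 score that is missing through the skip rule is passed over in favour of the screening score.

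**Working it through.** The documents state no figure for IDEEL, so there is none to reproduce. The check applies the SAP's own rules to one patient and then shows a range for the share affected.

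**Scoring.** Score = 25 × mean of the non-missing items, and not calculated if 3 or more of the 4 are missing. IDLTREAT=0 makes 4 of 4 missing, so there is never a score at that visit.

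**Example.** Take Week 4 items 3, 3, 2, 3: 25 × 11/4 = 68.75. Take pre-dose items, where scored, of 1, 1, 0, 1: 25 × 3/4 = 18.75.

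| IDLTREAT at screening | IDLTREAT on Day 1 | Change at Week 4, Day 1 score only | Change at Week 4, last non-missing pre-dose score |
|---|---|---|---|
| above 0 | above 0 | 50.0 | 50.0 |
| 0 | above 0 | 50.0 | 50.0 |
| above 0 | 0 | missing | 50.0 |
| 0 | 0 | missing | missing |

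Where the change is missing at Week 4 for lack of a baseline, it is missing at Weeks 8, 12 and 16 too. A repeated-measures model cannot use a patient with no response at any visit. A mixed model fitted to mock data for 228 patients, 40 of them without a baseline score, used 228 − 40 = 188 patients with change as response and all 228 with the observed score as response.

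**How far the screening score helps.** The wash-out is 7 to 9 days and the recall is 14 days, so the two recall periods overlap by about 14 − 9 = 5 to 14 − 7 = 7 days. The screening score helps only a patient whose reported use fell before that overlap, which is probably uncommon.

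**Size.** Let q be the share with no usable baseline, which is assumed. With equal loss across arms and an unchanged residual SD, the standard error is multiplied by 1/√(1 − q). Patient counts use the 228 evaluable patients in SAP 3.4.

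| q (assumed) | Patients lost of 228 | Standard error multiplied by |
|---|---|---|
| 5% | 11 | 1/√0.95 = 1.03 |
| 10% | 23 | 1/√0.90 = 1.05 |
| 20% | 46 | 1/√0.80 = 1.12 |

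**Treatment-Related Bother.** IDLTREAT=0 removes one of its four items (IDLTBO1), and the score is still calculated from three. Its other gate, IDLDRPYN, asks whether the patient ever uses eye drops. A 'No' removes three of four items, and the score is then lost.

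**The case against.** The strongest reply is that few patients may be affected and that no treatment comparison is distorted. Entrants have had dry eye diagnosed for at least 6 months, with tears in use or recommended. Tears stay available through the wash-out, and IDLTREAT=0 requires no treatment at all over two weeks. The screening score may also stand in. All of this stands, and it limits the size of the point. It does not remove the mechanism for a patient who reports no use at both visits.

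A reader might infer that the arm comparison is biased. The documents do not support that. The missing baseline precedes randomisation, so it is balanced in expectation. The same holds for the product rated at baseline, so a between-arm contrast in change remains valid among patients who have a baseline.

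A reader might also infer that Treatment-Related Bother is equally affected. It is not. Only patients who say they never use eye drops are sure to lose that score, and in this population they are likely to be few.

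It can also be said that observed scores do not measure satisfaction with study drops throughout. This is correct after Week 4. Protocol 6.2 has all patients on sponsor-supplied tears three times daily in follow-up, so with two-week recall Weeks 8, 12 and 16 rate those tears.

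Finally, Work Limitations also has a gate (IDLWRKYN). There, however, assigned study treatment does not turn a patient without a score into one with a score, so the argument made here does not carry over directly.

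**Conclusion.** The point holds for Treatment Satisfaction/Happiness. Under the SAP's rules, a patient with IDLTREAT=0 at both screening and Day 1 is dropped from the analysis despite a complete Week 4 score. If a Day 1 score missing through the skip rule is not passed over, IDLTREAT=0 on Day 1 alone is enough.

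The consequence is lost precision and a narrower population, with no arm bias expected. The documents do not show how many patients this concerns. The increase of about 3% to 12% in the standard error rests on an assumed 5% to 20% share and an unchanged residual SD. It is the cost of dropping those patients, not the exact gain from the fix, which also changes the response and adds covariates.

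The matter concerns one of six scales within one of eight secondary endpoints, with a probably small extension to a second scale. The primary analysis is untouched.

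**What to change.** For Treatment Satisfaction/Happiness, amend SAP 8.2.6 and the sample code as follows:

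1. Use the observed post-baseline score as the MMRM response. Keep treatment, visit and their interaction. Add as covariates the baseline score (set to a constant where absent) and an indicator for no baseline score. Both are fixed before randomisation, so adjusting for them does not bias the arm comparison.
2. State that baseline is the last non-missing pre-dose score, screening included.
3. Report the number of patients without a baseline score by arm.
4. Name Week 4 as the visit that measures satisfaction with study drops, and label Weeks 8 to 16 as ratings of the follow-up tears.

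The same model can serve Treatment-Related Bother. SAP Section 11 already records a change to the IDEEL analysis and can carry this one.

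The cost is a few sentences, one changed response variable, two covariates and a slightly different presentation from the other IDEEL scales. The change does not recover a post-baseline score that is itself missing because the patient reports no treatment at that visit.
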